3.4.1.1. Treatment Compliance

Study drug compliance will be calculated as:

$$\frac{100 \times 0.5 \times (\text{number of capsules dispensed} - \text{number of capsules returned})}{(\text{date of last dose} - \text{date of first dose} + 1)}$$

Study drug compliance over the interval from first to last dose will be summarized as a continuous variable and by rounding to the nearest 0.1% and showing counts and percentages for the following disjoint categories: $\geq 120\%$; 110% to 120%; 90% to 110%; 80% to 90%; $< 80\%$.

Study drug administration information (date/time and study day) will be provided in a data listing. Study drug accountability information and study drug exposure and compliance will also be provided in data listings.

Study drug discontinuations and reasons for study drug discontinuation will be listed.

3.4.2. Adverse Events

Adverse events (AEs) will be coded to the preferred terms (PT) of the Medical Dictionary for Regulatory Activities (MedDRA®). Summaries will be presented by system organ class (SOC), preferred term, and severity and/or relatedness, the number and percentage of subjects for whom events were reported.

Adverse events (AEs) are recorded from signing of the informed consent form through the final follow-up assessment. Adverse events observed prior to first dose are non-treatment emergent.

Treatment emergent adverse events are defined as follows:

- TEAEs are AEs with onset on or after the first initiation of study drug up to the date of last dose of study drug + 28 days.

Only treatment-emergent AEs will be summarized in the tables. A listing of all TEAEs by subject will be provided.

An AE will be considered a treatment emergent serious AE (TESAE) if it is a TEAE that additionally meets any SAE criteria.

If more than 1 AE is coded to the same preferred term for the same subject, the subject will be counted only once for that preferred term using the most severe and most related occurrence for the summarizations by severity and by relationship to study drug.

Summary tables will also be provided for subjects with:

- TESAEs by SOC and PT
- TEAEs leading to discontinuation of study drug by SOC and PT
- TEAEs leading to temporary interruption of study drug by SOC and PT

- TEAEs by severity and by SOC and PT
- Drug related TEAEs by severity and by SOC and PT

Listings of all AEs, SAEs, AEs resulting in death, and AEs leading to discontinuation by subject will be presented.

An overall summary of adverse events will also be presented and will include the following summary lines: Any AE, Moderate or Severe AEs, AEs Related to Study Drug, Moderate or Severe AEs Related to Study Drug, Serious AEs, Serious AEs Related to Study Drug, AEs Leading to Premature Study Drug Discontinuation, AEs Leading to Temporary Interruption of Study Drug, and Deaths During Study.

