#### 7.1.1. Adverse Events (AE)

An AE on Protocol 0164 (LTS) is any AE that occurs after the first dose of study drug. An AE prior to the first dose of study drug on Protocol 0164 (LTS) will be documented in the 0157 Study and if continuing at the time of consent to Protocol 0164 (LTS), the AE will be documented in the Protocol 0164 (LTS) database as an ongoing event.

An AE is any untoward medical occurrence in a patient or clinical trial subject administered a pharmaceutical product that does not necessarily have to have a causal relationship with this treatment. An AE can therefore be any unfavorable and unintended sign (including an abnormal laboratory finding), symptom, or disease temporally associated with the use of a medicinal product, whether or not related to the medicinal product.

- AEs may be new events
- Preexisting events that increase in frequency, severity or change in nature or seriousness during or as a consequence of participation in clinical studies.
- Pre- or post-treatment complications that occur as a result of a protocol-mandated procedure [REDACTED]
- AEs may be clinically significant changes from baseline in physical examination, laboratory tests, or other diagnostic investigation (e.g., laboratory results, x-ray findings).
- AEs may result from an overdose of the Study drug.

Whenever possible, the diagnosis (rather than a series of terms related to a diagnosis) should be recorded as the AE term.

An AE does not include the following:

- Medical or surgical procedures (such as surgery, [REDACTED], tooth extraction, or transfusion); the condition that leads to the procedure is an adverse event
- Preexisting diseases or conditions present or detected before signing an informed consent form that do not worsen
- Situations where an untoward medical occurrence has not occurred (such as hospitalization for elective surgery or social and/or convenience admissions)
- Overdose of either Study drug or concomitant medication without any signs or symptoms, unless the subject is hospitalized for observation

Any medical condition or clinically significant laboratory abnormality with an onset date prior to the time the subject signed the informed consent form is considered to be preexisting and should be documented in the medical history CRF.

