### 8.6.1. Adverse Event Data

Adverse events will be coded using the Medical Dictionary for Regulatory Activities (MedDRA®). Summaries will present by system organ class (SOC), preferred term (PT), and severity, the number and percentage of subjects reporting each observed event.

A treatment-emergent adverse event (TEAE) is defined as any AE with a recorded start date on or after the date of the first dose of LTS study drug up through 4 weeks after the last dose of study drug. Treatment-emergent status of AEs with a partial start date will be determined using available date information. If the available date information is inconclusive or no date information was recorded, the AE will be classified as LTS treatment-emergent.

All TEAEs will be listed by subject, and a separate listing of AEs classified as not LTS treatment-emergent (i.e., ongoing at entry) will be provided. Numbers of subjects who experienced TEAEs will be summarized overall and by arm. TEAEs will also be summarized by relationship to treatment (study drug) and severity, and by duration of exposure categories to be specified in the SAP.

A listing will be provided for all subjects who experience an SAE. Listings will also be provided for subjects who discontinued study treatment because of AEs, subjects who temporarily interrupted study treatment because of AEs, and subjects who experienced AESIs.

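### TEAEs are defined by onset date alone, so an AE carried over from Study 0157 that worsens or becomes serious on LTS drug drops out of the TEAE and TESAE tables unless the site entered the worsening as a new record

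*SAP*

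**What the plan says.** Four rules bear on this point.

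- **What counts as an AE (Protocol 7.1.1).** The definition takes in "Preexisting events that increase in frequency, severity or change in nature or seriousness during or as a consequence of participation in clinical studies". Among conditions present before consent, it leaves out only those that do not worsen.
- **How a carried-over event is recorded (Protocol 7.1.1).** If an AE from Study 0157 is still continuing at consent to the LTS study, "the AE will be documented in the Protocol 0164 (LTS) database as an ongoing event".
- **What counts as treatment-emergent.** Protocol 8.6.1 requires "any AE with a recorded start date on or after the date of the first dose of LTS study drug", up to 4 weeks after the last dose. It sends events ongoing at entry to a separate listing as not LTS treatment-emergent. SAP 3.4.2 says "TEAEs are AEs with onset on or after the first initiation of study drug", with the window closing at the last dose plus 28 days, and adds: "Adverse events observed prior to first dose are non-treatment emergent".
- **What is tabulated (SAP 3.4.2).** "Only treatment-emergent AEs will be summarized in the tables". For serious events: "An AE will be considered a treatment emergent serious AE (TESAE) if it is a TEAE that additionally meets any SAE criteria". Listings are wider and cover all AEs, SAEs, AEs resulting in death and AEs leading to discontinuation.

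SAP Appendix 1, the list of changes to protocol-planned analyses, mentions only the dropped efficacy analyses.

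**The concern.** Incidence and severity of TEAEs come first in the primary endpoint (Protocol 3.3.1 and synopsis). Every subject rolls over from an earlier study of the same drug, so AEs ongoing at entry follow from the design, and Protocol 8.6.1 plans a listing for them. The AE definition treats worsening as an event in its own right, but neither TEAE definition does.

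Laboratory values, vital signs and ECGs are all summarised as change from baseline (SAP 3.4.3), so deterioration of an existing abnormality shows in those outputs. AEs are the one component of the primary endpoint where the written rules do not secure this. What is at stake is some understatement of incidence, severity and seriousness in the tables from which the safety conclusion will be read.

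**Working it through.** No formula applies, and the plan states no figure to reproduce. The check is to take one event through the written rules.

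**Test case.** A subject has a non-serious infection with onset during Study 0157, still ongoing at LTS Day 1. On LTS drug it worsens and the subject is hospitalised for it. The worsened event meets the hospitalisation criterion for an SAE (Protocol 7.1.2) and the serious-infection category of AESI (Protocol 7.1.4).

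1. **Recording.** Under Protocol 7.1.1 the infection is in the 0164 database as an ongoing event, with its onset before the first LTS dose.
2. **TEAE status.** Onset precedes the window in both Protocol 8.6.1 and SAP 3.4.2. Neither has a clause for later change, so the record is non-treatment-emergent whatever happens to it afterwards.
3. **Tables built explicitly on TEAEs or TESAEs (SAP 3.4.2).** The record is absent from the tables by SOC and PT, by severity, for drug-related events, for TESAEs, and for TEAEs leading to discontinuation or temporary interruption. Becoming serious does not bring it in, because a TESAE must first be a TEAE.
4. **Summaries not labelled as TEAE.** These are the overall summary lines (any AE, serious AEs, deaths), the AESI incidence summary in SAP 3.4.2.1, and the tables in SAP 3.4 for deaths, non-fatal SAEs and discontinuations. The TEAE-only sentence in SAP 3.4.2 appears to exclude the record from these too, but the wording leaves some doubt.
5. **Listings.** The record appears in those for all AEs and SAEs, and in those for deaths or discontinuations where relevant.
6. **Other provisions.** The rule of counting a subject once per preferred term at the most severe occurrence works within TEAEs, so it does not bring the record back. The start-date imputation in SAP 5.2.2.1 follows the same onset logic. Appendix 1 does not address the matter.

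**Which first dose.** SAP 3.4.2 does not say that the first initiation of study drug means LTS drug. Protocol 8.6.1 does say so, and the SAP's treatment of AEs before first dose fits that reading, which is the one used here.

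**Size.** The share of subjects losing a TEAE on this account would be

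P(AE ongoing at first LTS dose) × P(it worsens in the window, given ongoing) × P(the worsening was not entered as a new record).

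The effect on the any-TEAE line would be smaller still, because a subject with another TEAE is counted anyway. The documents give none of these quantities, so no estimate is possible.

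**The case against.** The strongest reply is that the protocol already allows worsening to be counted. Protocol 7.1.1 describes a 0164 AE as one occurring after the first dose of study drug and names worsening of a preexisting event as an AE. Protocol 7.3 asks for onset date and severity for each AE, and Protocol 7.4.2 requires all AEs to be recorded from consent. A site could therefore enter the worsening as a new AE with its own onset date, and that record would be a TEAE. Completion instructions for the case report form, which are not among the documents, may even have required it.

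This stands in part. It limits the problem to events kept under their original onset date. It does not remove it, because nothing in the protocol or SAP requires a new record or says how a change in severity is to be dated. As written, the count depends on site practice.

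It is also true that listings show the event, that SAEs additionally go on an SAE Report Form, and that the output is a descriptive synoptic report without inferential tests. Those points limit the consequence. Incidence is still read from tables.

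A reader might go further in three ways that the documents do not support.

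- *Every worsened carried-over event is missing from every AE table.* The new-record route and the summaries not labelled TEAE make this too absolute. A line for deaths during the study might in practice count every death.
- *The loss falls mainly on subjects entering without remission, and so differs by dose.* Dose does depend on remission status and prior dose (SAP 1.2). But neither document says that loss of response or UC activity is recorded as an AE, so these subjects are not shown to carry more ongoing AEs.
- *A percentage can be put on the undercount.* Any figure would be a product of assumed fractions with no anchor in the documents.

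**Conclusion.** The gap is real and shared by both documents. The SAP follows the protocol's TEAE rule, and that rule is narrower than the protocol's own AE definition. For a carried-over AE kept under its original onset date, exclusion from the TEAE and TESAE tables follows directly from the text. Exclusion from the overall and AESI summaries follows only if the TEAE-only sentence governs them, which is the more natural reading but not certain.

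The size is unknown. The conclusion assumes that the first initiation of study drug in the SAP means the first LTS dose, and that at least some worsening was not entered as a new record. The matter deserves correction because it touches the primary endpoint and the analysis change is small.

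**What to change.** In SAP 3.4.2, define a TEAE as an AE that either

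- has onset on or after the first LTS dose, or
- has earlier onset and increases in severity, seriousness or frequency on or after that dose,

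in both cases up to the last dose + 28 days.

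Apply the second limb using the recorded severity, seriousness and action taken. Where the date of worsening was not captured, at minimum add a table of AEs ongoing at first LTS dose that became serious, led to discontinuation or interruption, or were fatal during LTS. State whether the overall and AESI summaries use the same definition. Record the change in SAP Appendix 1 as a departure from Protocol 8.6.1. The rule itself belongs in 3.4.2, because the SAP says its appendices are not a formal section of the signed plan.

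Telling sites to open a new record at worsening would no longer help: SAP section 1 puts all last doses by 09SEP2021 and all end-of-study visits by 11OCT2021.

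The cost is a clause in the SAP, some programming and possibly one extra table. TEAE counts will rise slightly. Some worsening dates or earlier severities may not be recoverable, and the report should say so.

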3.4.2.1. Adverse Events of Special Interest

An AE of special interest (AESI) is one of scientific and medical interest specific to understanding the investigational product and may require close monitoring and rapid communication by the investigator to the sponsor. The following are the AESI's defined for the study:

- Suspected or Confirmed Intestinal Perforation
- Complicated Herpes Zoster (multi-dermatomal, disseminated, or with ophthalmic or CNS involvement)
- Malignancy excluding non-melanoma skin cancer
- Non-melanoma skin cancer
- Serious Infection (e.g., that requires hospitalization or intravenous antimicrobials)
- Opportunistic Infections
- Thromboembolic disease (e.g. deep vein thrombosis, pulmonary embolism)
- Clinical Laboratory Abnormalities of Concern
- Major Cardiovascular Event (e.g. myocardial infarction or cerebrovascular accident)

The incidence of AESI's will be summarized overall and by AESI category and preferred term.

3.4.3. Additional Safety Assessments

3.4.3.1. Clinical Laboratory Parameters

Laboratory data, hematology, serum chemistry and urinalysis, will be summarized in terms of observed values and changes from baseline. In addition, changes from baseline relative to normal ranges from the central lab (e.g., shifts from normal to abnormal high/low) will be summarized.

The number and percentage of subjects with clinically abnormal lab values will also be summarized by timepoint for the following criteria:

- absolute neutrophil count of $< 1.0 \times 10^9/L$

- white blood cell count of $< 2.0 \times 10^9/L$
- absolute lymphocyte count of $< 0.5 \times 10^9/L$

A listing of all abnormal lab values will be provided.

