### 1.5. Risks and Benefits

TD-1473 is being evaluated for the treatment of inflammatory intestinal disorders. Treatment with tofacitinib, a systemic pan-JAK inhibitor, has demonstrated to result in statistically significantly higher rates of remission compared to placebo. However, given limited data from the Phase 1b Study in a small number of subjects with moderately-to-severely active UC treated with TD-1473 for 4 weeks, efficacy with TD-1473 in UC has not been established.

Some patients receiving repeated doses of tofacitinib, a systemic JAK inhibitor, have exhibited alterations in cholesterol (LDL, HDL, and total cholesterol), liver function tests, serum creatinine, decreased red blood cell and white blood cell (particularly neutrophils and lymphocytes) counts, infection (particularly herpes zoster and tuberculosis), cancer (including lymphoma), intestinal perforation, and thromboembolic events. In addition to these, diarrhea and rash have also been reported. However, given the anticipated relatively low systemic exposure of TD-1473, these risks are anticipated to be minimal in the current study.

In the Phase 1 Study in healthy volunteers, all treatment-emergent adverse events (TEAEs) in subjects dosed with TD-1473 (most commonly noted were headaches at 100 mg and 300 mg with similar or lower prevalence as placebo) were mild in severity and short in duration. In the Phase 1b Study in UC subjects, TD-1473 was generally well tolerated with only two adverse events (urticaria at 80 mg and papular rash at 20 mg) deemed by the Principal Investigator (PI) to be possibly related to study drug; the adverse events were considered mild in severity, in both cases and resolved within a few days after the last dose of study drug. No adverse event led to drug interruption or discontinuation. Similar to the healthy volunteer study, there were no adverse alterations in vital signs, electrocardiogram parameters, or laboratory evaluations relative to placebo. There have been additional Phase 1 studies in healthy volunteers that, together, have not yielded a repeated pattern of TEAEs frequently observed in every study.

The potential risks described in this section will be carefully assessed during the Study. Assessments include scheduled physical exams, and frequent monitoring of complete blood cell counts with differential, kidney and liver function, creatinine phosphokinase, and fasting cholesterol panel.

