**6.4.1.14. Overnight Fasting Lipid Panel**

Fasting low-density lipoprotein (LDL), high-density lipoprotein (HDL), triglyceride, and total cholesterol will be measured at the time points designated in Schedule of Study Procedures (Table 1). Subject must fast from food and non-clear fluids for a minimum of 8 hours overnight prior to blood collection.

Detailed instructions and collection kits for sample collection, handling, and shipping will be provided by the central laboratory.

[REDACTED]

[REDACTED]

[REDACTED]

[REDACTED]

[REDACTED]

[REDACTED]

[REDACTED]

[REDACTED]

[REDACTED]

[REDACTED]

[REDACTED]

[REDACTED]

[REDACTED]

[REDACTED]

[REDACTED]

[REDACTED]

[REDACTED]

- [REDACTED]
- [REDACTED]
- [REDACTED]

[REDACTED]

[REDACTED]

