## 8.6. Safety Analyses

Safety variables to be summarized include vital signs, adverse events, clinical laboratory results (hematology, chemistry, overnight fasting lipid panel), and 12-lead ECG intervals, including QT interval corrected for heart rate using Fridericia's formula (QTcF).

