### **8.6.3. Laboratory Data**

Safety laboratory values and C-reactive protein values, changes from baseline, values relative to normal ranges, and clinical laboratory abnormalities of concern will be summarized by visit, overall and by arm. C-reactive protein, [REDACTED] total cholesterol, LDL, HDL, and triglycerides levels will be log-transformed for summarization.

Reference ranges provided by the laboratory for each test will be used to evaluate the clinical significance of laboratory test results. Values falling outside the relevant reference range will be flagged, as appropriate, in the data listings. Clinical laboratory abnormalities of concern will be listed in a separate listing. A listing of pregnancy test results will be provided.

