1.4. Schedule of Assessments

Table 4: Schedule of Study Procedures

Study Procedures	Day 1	WEEK VISITS +/- 5 Days								Early Study Drug Discontinuation ^l + 5 days from last dose	EOS 4 Weeks Post Last Dose ^l - 3 to + 5 days
		Year 1	W4	W12		W24	W36	W48	W52		
		Year 2			W60	W72	W84	W96	W104		
		Year 3			W108	W120	W132	W144	W156		
Informed Consent	X										
Review Inclusion/Exclusion Criteria	X										
Physician Global Assessment (PGA)	X		X	X	X	X	X	X	X	X	X
Pregnancy Test (females of child-bearing potential)	X		X ^e	X ^e	X ^e	X ^e	X ^e	X ^e	X ^e	X ^e	X ^e
FSH	X ^a										
████████████████████	■			■		■		■		■	■
In Clinic Dosing - Study Drug Dosing	X ^k										
Vital Signs (Temp, HR, BP, Respirations)	X ^l		X ^l	X ^l	X ^l	X ^l	X ^l	X ^l	X ^l	X	X
Safety Laboratory (Chemistry, Hematology)	X ^{a, m}		X	X	X	X	X	X		X	X
Physical Exam	X ^a		X	X	X	X	X	X	X	X	X
Smoking Status	X ^a								X		X
Weight	X ^a								X		
Medical History / Demographics	X ^{a, b}										
Concomitant Medication /Adverse Event Review	X		X	X	X	X	X	X	X	X	X
Overnight Fasting Lipid Panel			X	X	X	X	X	X		X	X
████████████████████	■		■	■	■	■	■	■	■	■	■
████████████████████									■		
████████████████████									■		
12-Lead Electrocardiogram (ECG)	X ^a			X				X	X		
Study Drug Dispensing	X		X	X	X	X	X	X	X ^e		
Study Drug Accountability			X	X	X	X	X	X	X	X	
Subject eDiary Daily Compliance Review			X ^h	X ^h							
Subject Symptom Recall and Compliance Review					X ⁱ	X ⁱ	X ⁱ	X ⁱ	X ⁱ	X ⁱ	
Dispense Subject eDiary	X ^h										
Return of Subject eDiary				X ^a							

Non-Site Study Procedures (Calculations for Programming/Statisticians and applicable suppliers)											
			■	■	■	■	■	■	■	■	■
									■		

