5. SUPPORTING DOCUMENTATION

5.1. Appendix 1: Changes to Protocol-Planned Analyses

The protocol-planned efficacy analyses are not required for the synoptic CSR.

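### SAP 3.4.3.1 omits the fasting lipid summary that protocol 8.6 and 8.6.3 plan, and no readable SAP text declares it dropped

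*SAP*

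**What the plan says.** Protocol 8.6 gives the laboratory part of the safety variables to be summarised as "clinical laboratory results (hematology, chemistry, overnight fasting lipid panel", with lipids named beside chemistry. Protocol 8.6.3 asks for safety laboratory summaries by visit, overall and by arm, and adds that "total cholesterol, LDL, HDL, and triglycerides levels will be log-transformed for summarization".

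SAP 3.4.3.1 is narrower on lipids: "Laboratory data, hematology, serum chemistry and urinalysis, will be summarized in terms of observed values and changes from baseline". It adds shifts relative to the normal range, counts for three blood-count thresholds, and a listing of abnormal values. In the readable SAP, lipids appear only as the row "Overnight Fasting Lipid Panel" of the schedule in SAP 1.4.

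On changes from the protocol, SAP Appendix 1 (5.1) has one statement: "The protocol-planned efficacy analyses are not required for the synoptic CSR". SAP section 1 keeps the safety endpoints within the synoptic report.

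**The concern.** This is a safety study whose report will contain safety results only, so the laboratory summaries are part of its main output. Protocol 1.5 says that some patients given tofacitinib, a systemic JAK inhibitor, "have exhibited alterations in cholesterol (LDL, HDL, and total cholesterol", along with other changes. It then includes the fasting cholesterol panel among the assessments by which the section's risks will be followed.

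If the SAP is programmed as it stands, that panel gets no table of observed values, changes or shifts. A listing shows each subject's results and flags abnormal ones. It does not readily show a shift in the mean or median within the normal range, or a gradient across the 20, 80 and 200 mg arms. Those are the patterns that a by-visit, by-arm summary is meant to show.

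**Working it through.** No power, alpha or sample-size figure is involved, and the SAP plans no inferential tests. The check compares the texts and counts scheduled visits.

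**1. Scope of the summaries, side by side**

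| Panel | Protocol 8.6 / 8.6.3 | SAP 3.4.3.1 | Readable schedule row |
|---|---|---|---|
| Hematology | yes | yes | yes |
| Chemistry | yes | yes | yes |
| Fasting lipids | yes, log scale | not named | yes, own row |
| Urinalysis | not named | yes | none readable |

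**2. Could serum chemistry include lipids?** Protocol 6.4.1.13 lists the chemistry analytes, and none is a lipid. Protocol 6.4.1.14 is a separate section: "Fasting low-density lipoprotein (LDL), high-density lipoprotein (HDL), triglyceride, and total cholesterol will be measured at the time points designated". The schedule separates them as well, with one row for "Safety Laboratory (Chemistry, Hematology" and another for the lipid panel. If a programmer pooled the two anyway, the log transformation would still be missing.

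**3. Is the omission declared?** Protocol 8.1 says that changes to its planned analyses will be described in the SAP. Appendix 1 of the SAP mentions efficacy only. Elsewhere the SAP body marks dropped items, such as enrollment (3.2.1) and subgroups (3.5.2), as not applicable to the synoptic report. The lipid summary carries no such mark.

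**4. How much collection is affected?** Lipid cells in the schedule (protocol Table 1, SAP Table 4):

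- Year 1: weeks 4, 12, 24, 36, 48 = 5
- Year 2: weeks 60, 72, 84, 96 = 4
- Year 3: weeks 108, 120, 132, 144 = 4
- Total: 5 + 4 + 4 = 13

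The scheduled visits after Day 1 are these 13 plus weeks 52, 104 and 156, so 13 + 3 = 16. The share with a lipid draw is 13/16 = 81%. Early Study Drug Discontinuation and End of Study also have one.

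This is the full three-year schedule. SAP section 1 says that the study was terminated early, with all last doses by 09SEP2021. The documents do not say how many of the 13 visits subjects reached.

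**5. Baseline.** The lipid row is blank at Day 1. SAP 3.1.1 takes baseline from the last pre-dose time point at which the schedule calls for the variable, and this study schedules none for lipids. SAP 5.2.2.4 replaces a missing laboratory baseline with the last available assessment, generally screening, but the first visit of this study is Day 1. Neither section says whether a Protocol 0157 lipid value may serve. Observed values by visit need no baseline; changes do.

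**The case against.** Several points can fairly be made against the concern.

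- **The data are not lost.** SAP 3.1 lists all individual data, 3.1.4 says all results go into listings, and 3.4.3.1 lists abnormal laboratory values. This stands: what is missing is the summary.
- **The SAP sentence opens with laboratory data in general, so lipids might be implied.** The three panels that follow read as the content of that term, and lipids are not among them. The log scale is absent on either reading.
- **Appendix 1 is weak evidence.** SAP section 1 says the appendices are not a formal part of the signed SAP, and Appendix 1 does not list the enrollment and subgroup summaries that the body drops. This stands in part. The case does not rest on Appendix 1 alone, because no readable part of the SAP drops lipids.
- **The risk is expected to be small.** Protocol 1.5 anticipates minimal risk because systemic exposure is low, and lipids are not among the adverse events of special interest or the example laboratory abnormalities of concern. This stands and limits the severity. The same section still commits to assessing these risks, including by the fasting panel.

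A reader might go further and infer that the SAP has replaced lipids with a panel for which no data exist. The documents do not support that. Schedule rows are redacted in both documents, and protocol 6.4.3.6 points to a Section 6.4.1.15 that cannot be read. Protocol 6.4.3 names urine safety tests among measures collected from all subjects, which a pregnancy test limited to females of childbearing potential would not satisfy. The absence of urinalysis from protocol 8.6 does not settle it either: that list also omits C-reactive protein, which 8.6.3 summarises.

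**Conclusion.** The lipid point holds on unredacted text. The protocol plans a log-scale lipid summary, the SAP does not name one, and the readable SAP does not declare the change. The consequence is the loss of a summary for a panel scheduled at 13 of 16 post-Day-1 visits plus two exit visits, with the number of visits actually reached unknown. It should be repaired before the tables are produced, but it does not threaten the study's other safety results.

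The conclusion assumes that the redacted parts of the SAP contain no lipid analysis; the laboratory section itself is readable. The separate table and listing specifications mentioned in SAP section 1 were not among the documents and might contain a lipid table. If so, the SAP text should be brought into line with them.

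On urinalysis, the documents support only a question to the sponsor. They do not show that it was not collected, so they give no ground for deleting it outright.

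**What to change.** In SAP 3.4.3.1, add the overnight fasting lipid panel (total cholesterol, LDL, HDL, triglycerides), summarised on the log scale by visit, overall and by arm, as protocol 8.6.3 intends. State the baseline source for any change from baseline, for example the last Protocol 0157 value before the first LTS dose if one exists; otherwise present observed values only. If the sponsor prefers to drop the summary, the SAP should say so and give the reason.

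Separately, ask the sponsor to confirm whether urinalysis was collected, and keep or delete that word in 3.4.3.1 accordingly. The protocol wording needs no change.

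The cost is a paragraph of SAP text and one further laboratory table from data the schedule already collects. No new sample is needed.
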